#### **4.3.2 Administration of ipilimumab**

Ipilimumab is to be administered as an IV infusion with a 1.2 µm in-line filter (see current version of Investigator's Brochure), using a volumetric pump, at the 3 mg/kg dose, and at an appropriate rate to complete the infusion in 90 minutes with a 10 cc normal saline flush at the end. Additional details on ipilimumab dose are outlined above in Section 4.1.1.1. Refer to Section 4.3.8.1 regarding management of infusion reactions.

#### **4.3.3 Dose Limiting Toxicity**

For the purpose of guiding dose escalation decision making, hematologic and non-hematologic (hepatic versus non-hepatic) DLT will be defined separately and will be determined based on the incidence, severity, and duration of **study drug-related** AEs occurring within 84 days (12 weeks; through Day 42 of induction cycle 2) of initiation of study therapy. Using these features, the severity of AEs will be graded according to the NCI Common Terminology Criteria for Adverse Events (CTCAE) Version 4.0. For the purposes of subject management, DLTs will lead to dose modification regardless of the cycle in which a DLT occurs (see Section 4.3.8 for specific guidelines).

##### **4.3.3.1 Definition of non hematologic dose-limiting toxicity**

Non-hematologic dose-limiting toxicity (DLT) will be defined as follows:

##### **A: Hepatic Non-Hematologic DLT**

Any one of the following events will be considered a hepatic DLT (irrespective of whether it is considered to be an irAE):

Isolated Grade 4 AST/ALT

Isolated Grade 3 AST/ALT that fails to return to Grade 1 or less within 5 days

Isolated Total Bilirubin  $\geq$  Grade 3 with AST or

ALT  $>$  3 x ULN and concurrent total bilirubin  $>$  2 x ULN

##### **B: Non-Hepatic Non-Hematologic DLT**

Any Grade 3 or greater non-hepatic non-hematologic toxicity will be considered as a dose-limiting toxicity with the following specific **exceptions**:

- Grade 3 electrolyte abnormalities that are not complicated by associated clinical adverse experiences, last less than 48 hours and either resolve spontaneously or respond to conventional medical intervention.
- Grade 3 nausea or vomiting that lasts less than 48 hours, and either resolves spontaneously or responds to conventional medical intervention.
- Isolated Grade 3 elevation of amylase or lipase not associated with clinical or radiographic evidence of pancreatitis.
- Isolated Grade 3 fever that lasts  $\leq$  3 days and is not associated with hemodynamic compromise (ie hypotension, clinical or laboratory evidence of impaired end-organ

perfusion).

**Criteria for Non-Hematologic DLT in Context of Immune-Related AEs and Infusion Reactions:**

A constellation of immune-related adverse events (irAEs) have been observed in patients treated with ipilimumab monotherapy. Similarly, as has been seen with a broad range of therapeutic antibodies, infusion reactions have been observed among patients treated with ipilimumab. Based on broad clinical experience with ipilimumab, a unique set of criteria have been developed to define and manage dose-limiting toxicities in the context of irAEs and/or infusion reactions and are outlined below.

**C: Immune-related Adverse Experiences (irAEs) and DLT**

Definition of DLT in the context of irAEs will consider the incidence, severity, time of onset, duration and time to resolution for the specific irAE in the context of existing experience with ipilimumab. All Grade 3 or greater immune related AEs will be considered as potential DLTs. An independent DMC will be utilized to advise on aggregate safety data from this study and more specifically to review all Grade 3 or greater irAEs. Immune related AEs among patients treated with ipilimumab have clustered among skin, gastrointestinal, endocrine and liver-related events as follows:

Skin: alopecia, dry skin, hyperhidrosis, night sweats, pruritus, rash/desquamation, toxic epidermal necrolysis, urticaria, and vitiligo.

Gastrointestinal: abdominal discomfort or pain, anal ulcer, colitis (including ulcerative, haemorrhagic, ischaemic, and megacolon), constipation, cramping, diarrhea (including haemorrhagic), diverticulitis/diverticulum, duodenitis, dyspepsia, dysphagia, enteritis, esophagitis, gastritis (including erosive), gastrointestinal haemorrhage (including rectal), hematochezia, ileitis, ileus, intestinal obstruction, intestinal perforation (including small and large intestines), melena, nausea, pancreatitis, peritonitis, stomatitis (including aphthous), vomiting, vasculitis gastrointestinal.

Endocrine: adrenal insufficiency (including Addison's disease), glucose tolerance impaired, hyperthyroidism hypogonadism, hypophysitis/hypopituitarism (autoimmune), hypothyroidism, pituitary enlargement, thyroiditis (autoimmune).

Liver: hepatitis, jaundice

**Dose-limiting immune-related AEs will be defined as the follows:**

- Any Grade 2 or greater eye pain or reduction in visual acuity that does not respond to topical therapy and does not improve to Grade 1 severity within 2 weeks of the initiation of topical therapy **or** any Grade 2 or greater eye pain or reduction in visual acuity that requires systemic treatment.
- Any other Grade 3 or greater irAE:

**D: Infusion Reaction and DLT**

Grade 3 or Grade 4 infusion reactions will also be considered as dose-limiting events.

**4.3.3.2 Definition of hematologic DLT**

Hematologic DLT will be defined as follows:

- Grade 4 neutropenia  $\geq$  7 days in duration
- Grade 4 thrombocytopenia, or any Grade 3 thrombocytopenia associated with clinically-significant bleeding

- Grade  $\geq$  3 febrile neutropenia
- Grade  $\geq$  3 hemolysis

#### **4.3.4 Duration of Treatment**

Subjects may remain on study therapy until progressive disease as determined by immune-related response criteria (irRC), withdrawal due to toxicity, withdrawal of consent, or at the discretion of the investigator.

#### **4.3.5 Intra-subject Dose Escalation**

Intrasubject dose escalation for panobinostat or ipilimumab is not permitted in order to allow better evaluation of extended safety and efficacy at individual levels.

#### **4.3.6 Guidelines for Dose Modification**

Patients who have not experienced a dose-limiting toxicity may continue on therapy if, in the opinion of the investigator, they are experiencing clinical benefit (i.e. stable disease or objective response as determined by irRC). For patients who experience a dose-limiting hematologic or non-hematologic toxicity, therapy should be held/deferred pending resolution of the toxicity.

#### **Panobinostat/Ipilimumab Dose Modification Guidelines for Non-hematologic and Hematologic Events Other Than Infusion Reactions:**

- Patients who experience hepatic non-hematologic DLT irrespective of irAE or any Grade 3 or greater irAE will be removed from study with no further dose reduction.
- For patients who experience a first episode of non-hepatic non-hematologic DLT or a first episode of hematologic DLT, therapy may be reinitiated at the next lowest panobinostat/ipilimumab dose level as specified below in Table 4.3 if the event has resolved to less than or equal to Grade 1 in severity at the time the next cycle is due.
- For patients who experience a second episode of either hematologic or non-hepatic non-hematologic DLT, a second dose reduction may be performed as specified below for the successive cycle if the second dose-limiting event is distinct in nature from the first event and the event has resolved to less than or equal to Grade 1 in severity at the time the next cycle is due.
- In the event of a DLT, successive cycles of therapy may be delayed up to 14 days pending resolution of the toxicity to grade 1 or less in severity. Patients on dose level #1 will not be dose reduced in the event of DLT. Patients on dose level #2 will be allowed a maximum of 1 dose reduction, with the second occurrence of DLT necessitating removal from study.
- Any patient who develops significant irreversible (i.e. more than 2 weeks after the last dose of study drug) organ dysfunction (i.e., Grade IV non-hepatic non-hematologic toxicity) or anaphylaxis considered to be related to study drug will also be removed from study with no further dose reduction.
- All cardiac events should be treated as per the local standard of care and referred to a specialist if clinically indicated. The readings of ECGs will use the Fridericia correction: QTcF. Any final decisions concerning dose modifications or permanently discontinuing the patient from study drug due to QTcF prolongation will be based on the

assessment of the principal investigator. If a patient cannot be dosed due to prolonged QTcF for more than 7 days since last dose, patient should be discontinued from study.

**Table 4.2** Criteria for dosing delays, dose-reductions, and re-initiation of treatment due to study drug-related QTcF abnormalities

ECGs to be performed at specified time point	Abnormality Noted	Dose Modification Guideline - At any time during a cycle of therapy (including intended day of dosing)
Cycle 1 Day 1 dose modification criteria:		
Pre-dose on cycle 1, day 1 3 ECGs separated by at least 5 minutes, obtained prior to panobinostat dosing	Average QTcF > 450 msec	Check and correct the patient's serum potassium, magnesium, calcium and phosphorus immediately, as well as evaluate con-meds. Repeat 3 pre-dose ECGs. If the 3 pre-dose ECGs: Do not meet criteria again, discontinue patient from study. Do meet criteria for dosing; administer study drug treatment.

ECGs to be performed at specified time point	Abnormality Noted	Dose Modification Guideline - At any time during a cycle of therapy (including intended day of dosing)
Cycle 1 Day 5 dose modification criteria		
Pre-dose on cycle 1, day 5: 3 ECGs separated by at least 5 minutes, obtained prior to panobinostat dosing	Average QTcF: ≥ 480 msec to < 500 msec OR > 60 msec increase from baseline average	
Check and correct the patient's serum potassium, magnesium, calcium and phosphorus immediately, as well as evaluate con-meds.
 
Notify Sponsor and transmit to ERT immediately for prompt review.
 
Repeat 3 pre-dose ECGs.
 
If the 3 pre-dose ECGs:
 
Do meet criteria for dosing; administer study drug treatment.
 
Do not meet criteria again, delay dose until the next scheduled time point and repeat 3 pre-dose ECGs.
 
If the repeat 3 pre-dose ECGs:
 
Do not meet pre-dose ECG criteria again, discontinue patient from study.
 
Do meet pre-dose ECG criteria for dosing and QT prolongation is determined to be related to study drug, resume study drug treatment with a dose reduction of one dose level. If however, it was determined that the QT prolongation was secondary to electrolyte abnormalities or con-meds, continue at the same dose level. Repeat ECGs - pre-dose (x3) on the next scheduled dosing day.

	Average QTcF ≥ 500 msec	
Check and correct the patient's serum potassium, magnesium, calcium and phosphorus immediately, as well as evaluate con-meds.
 
Notify Sponsor and transmit to ERT immediately for prompt review.
 
Discontinue patient from study therapy
 
If however, it was determined that the QT prolongation was secondary to electrolyte abnormalities or con-meds: omit dose. On the next scheduled dosing day continue at the same dose level. Repeat ECGs - pre-dose (x3), 3-hours post-dose (x3), on the next scheduled dosing day.

ECGs to be performed at specified time point	Abnormality Noted	Dose Modification Guideline - At any time during a cycle of therapy (including intended day of dosing)
Cycle 2 and beyond dose modification criteria:		
If required: Pre-dose on day 1 of each cycle 3 ECGs separated by at least 5 minutes, obtained prior to panobinostat dosing:	Average QTcF > 480 msec	Check and correct the patient's serum potassium, magnesium, calcium and phosphorus immediately, as well as evaluate con-meds. If abnormality noted: Repeat 3 pre-dose ECGs. If the 3 pre-dose ECGs: Do not meet criteria again, discontinue patient from the study. Do meet criteria for dosing; administer study drug treatment If, however, it was determined that the QT prolongation was secondary to electrolyte abnormalities or con-meds: Omit dose. On the next scheduled dosing day, continue at the same dose level. Repeat ECGs pre-dose (x3) on the next scheduled dosing day.
	Average QTcF ≥ 500 msec	Check and correct the patient's serum potassium, magnesium, calcium and phosphorus immediately. Discontinue patient from study therapy If however, it was determined that the QT prolongation was secondary to electrolyte abnormalities or con-meds: omit dose. On the next scheduled dosing day continue at the same dose level. Repeat ECGs - pre-dose (x3) on the next scheduled dosing day.

In the setting where dose modifications are required, doses of PANOBINOSTAT and ipilimumab will be reduced to doses for the cohort immediately preceding the current dose level. Dose modifications are provided in Table 4.3

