#### **1.4.1.3 Non-clinical safety and toxicology**

Panobinostat has shown genotoxic potential in bacterial and eukaryotic systems. It has a preclinical signal for QT prolongation based on *in vitro* electrophysiological investigations and *in vivo* studies using telemeterized dogs. In the oral repeated doses toxicology studies, the primary target organs were identified as the erythropoietic, myelopoietic, and lymphatic system. Other secondary target organs included the gastrointestinal (GI) tract, reproductive system, thyroid and bone. Evidence of reversibility was observed for all white blood cells.

Oral administration of panobinostat to rats and rabbits is associated with embryo-fetal toxicity (increased resorptions/decreased live litters). Although no major malformations were observed, the incidence of fetal skeletal variations and anomalies was increased. Based upon the results of preclinical studies, hematology parameters, thyroid function and cardiac function assessments have been included in clinical trials. Panobinostat poses a reproductive risk to men and women of child bearing potential; therefore use of adequate birth control methods is required while a patient is on drug and for 12 weeks after the last dose.

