#### **1.4.1.4 Human pharmacokinetics and Safety**

In humans, panobinostat exhibits a linear PK profile following i.v. administration. panobinostat exposure is nearly dose- proportional at doses below 60 mg following oral administration; inter-patient variability in exposure (AUC) is 60% with oral and 40% with i.v. panobinostat (coefficient of variability [CV]). The drug has a rapid oral absorption  $T_{max}$  = 1 hour. Absolute bioavailability is 30% and elimination  $t_{1/2}$  is approximately 15 hours.

The clinical development of panobinostat has been conducted with both an i.v. and oral formulation The major dose-limiting-toxicity (DLT) for both formulations administered as a single agent is reversible thrombocytopenia. For the i.v. formulation, a weekly i.v. dosing scheme (Day 1, Day 8 every 21 days) is currently used in clinical studies with thrombocytopenia being managed by dose and schedule adjustment. For the oral formulation, a pooled analysis of data from phase I/II studies indicates that thrombocytopenia is the most common lab abnormality of any grade and of Grade 3-4 in patients treated with the three-times-a-week (TIW), every week (QW) and every-other-week (QOW) schedules. The median time to Grade 3 thrombocytopenia appears to be shorter with the QW dosing as compared with the QOW dosing. The magnitude of platelet count decline is dose-dependent and related to the baseline platelet count. The median time to recovery from severe thrombocytopenia, Grade 3-4 to Grade 2 or below, is approximately 8 days for doses up to 40 mg in solid tumors and lymphomas. The median time to recovery from severe thrombocytopenia is much longer (up to approximately 74 days) for doses up to 60 mg used in hematologic malignancies. Preliminary evidence in patients with solid tumors and lymphomas suggests that switching from the QW to the QOW schedule may be more effective than other dose modifications for reducing the recurrence of thrombocytopenic events

QT prolongation, a known class effect of HDAC inhibitors, appears to be formulation, dose and schedule dependent. For the i.v. formulation, QTcF prolongation of clinical relevance (Grade  $\geq 3$  with absolute increase  $>500$  msec) was seen in 4/15 patients (26.7%)

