#### **1.4.3 Rationale for Starting Doses of Panobinostat and Ipilimumab**

Based on data from the nonclinical pharmacology studies and monotherapy panobinostat studies the TIW dose regimen is hypothesized to result in target inhibition of HDAC activity while maintaining an acceptable safety profile. Therefore, the TIW dose regimen of PANOBINOSTAT has been selected for this study. In the ongoing monotherapy study, the 10 and 20 mg TIW dose cohorts have demonstrated adequate safety and tolerability. In this study, PANOBINOSTAT will be administered as a formulated capsule that has been used in the clinic. The major toxicities of PANOBINOSTAT, being thrombocytopenia and cardiac in nature, do not overlap with the major known side effects of ipilimumab. Both 3 and 10 mg/kg doses of ipilimumab have been associated with anti-tumor activity in melanoma subjects. Based on the potential for better tolerability, the lower, 3 mg/kg, dose has been selected as the starting dose of ipilimumab for this study.

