**Table 4.3 Dose Modification Guidelines for Panobinostat and Ipilimumab**

Cohort	Ipilimumab Dose Panobinostat Dose	Dose Modification #1	Dose Modification #2
1	3 mg/kg	1 mg/kg	Off Study
	5 mg	5 mg	
2	3 mg/kg	3 mg/kg	Off Study
	10 mg	5 mg	
3	3 mg/kg	3 mg/kg	3 mg/kg
	15 mg	10 mg	5 mg
4	3 mg/kg	3 mg/kg	3 mg/kg
	20 mg	15 mg	10 mg
-1	1 mg/kg	Off Study	Off Study
	5 mg		

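### In cohort 1, the Day 5 dose reduction for drug-related QTcF prolongation leaves panobinostat at 5 mg and cuts only ipilimumab

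*Combined protocol and SAP*

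**What the plan says.** Table 4.2, Cycle 1 Day 5, is triggered by an average QTcF of 480 to below 500 msec, or a rise of more than 60 msec from baseline. If the same-day repeat triplicate also fails, the dose is held to the next scheduled time point and the ECGs are repeated. If they then pass and the prolongation is attributed to study drug, the instruction is to "resume study drug treatment with a dose reduction of one dose level".

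The text after Table 4.2 defines a reduction: "doses of PANOBINOSTAT and ipilimumab will be reduced to doses for the cohort immediately preceding the current dose level". It refers to Table 4.3, "Dose Modification Guidelines for Panobinostat and Ipilimumab". The cohort 1 row there gives, as modification #1, ipilimumab 1 mg/kg with panobinostat 5 mg. This equals cohort -1 in Table 3.1.

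On which drug carries the risk, Section 1.4.1.3 says of panobinostat: "It has a preclinical signal for QT prolongation based on" laboratory and animal work. Section 1.4.1.4 adds: "QT prolongation, a known class effect of HDAC inhibitors, appears to be formulation, dose and schedule dependent". Section 1.4.3 states: "The major toxicities of PANOBINOSTAT, being thrombocytopenia and cardiac in nature, do not overlap with the major known side effects of ipilimumab".

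Two other sentences in Section 4.3.6 bear on the point. One is "Patients on dose level #1 will not be dose reduced in the event of DLT". The other, which begins "Any final decisions concerning dose modifications or permanently discontinuing the patient from study drug due to QTcF prolongation will be based on the", leaves the final QTcF decision to the principal investigator's assessment.

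**The concern.** A dose reduction after a drug-related toxicity should lower exposure to the drug thought to cause it. Here the generic one-level step is applied to a toxicity the protocol assigns to one drug, and in the starting cohort the level below differs only in the other drug. A cohort 1 subject with prolongation confirmed on repeat ECG would restart panobinostat at the same dose and schedule. The same subject would lose two thirds of each later ipilimumab dose, with no stated QT benefit.

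What is at stake is individual safety, and loss of ipilimumab exposure, in the first cohort of a combination that Section 1.4.4 says has not been evaluated in humans. The operating characteristics of the dose-finding rule are barely affected.

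**Working it through.** The plan gives no figure of its own here. The check is a look-up followed by simple arithmetic.

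**1. First reduction by cohort (Table 4.3)**

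| Cohort | Panobinostat, mg | Change | Ipilimumab, mg/kg |
|---|---|---|---|
| 1 | 5 to 5 | 0% | 3 to 1 (-67%) |
| 2 | 10 to 5 | -50% | 3 to 3 |
| 3 | 15 to 10 | -33% | 3 to 3 |
| 4 | 20 to 15 | -25% | 3 to 3 |
| -1 | Off Study | n/a | Off Study |

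Cohort 1 is the only row in which a first reduction leaves panobinostat unchanged. Elsewhere, a subject on 5 mg who needs a further reduction goes off study: cohort -1 at the first modification, cohort 2 at the second.

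**2. Ipilimumab exposure.** Infusions fall on Days 1 and 22 of each 42-day cycle (Section 3.1), so on study Days 1, 22, 43 and 64. Planned: 4 x 3 = 12 mg/kg. After a Day 5 reduction: 3 + 1 + 1 + 1 = 6 mg/kg, or -50%. The first infusion affected is Day 22.

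**3. Panobinostat doses given unchanged.** Assume dosing on Days 1, 3 and 5 of each week; the plan says only three times weekly. The Day 5 dose is held and dosing resumes on Day 8. That is 8 - 3 = 5 days after the last dose, inside the 7-day limit in Section 4.3.6.
- Before any dose changes on Day 22: Days 8, 10, 12, 15, 17 and 19, which is 6 doses of 5 mg.
- Table 4.2 asks for one repeat triplicate on the next dosing day (Day 10), reading that sentence as covering this branch. Table 5.12 then schedules no ECG until Cycle 2 Day 1 (Day 43). Doses from Day 10 to Day 40: 2 + 4 x 3 = 14.

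**4. Does the dose level #1 sentence remove the problem?** It is limited to DLTs. Section 1.4.1.4 pairs Grade 3 or higher QTcF prolongation with more than 500 msec, so the sentence does not reach the 480 to below 500 msec trigger. If it were applied, panobinostat would still stay at 5 mg.

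**5. Frequency.** The only rate in the documents is QTcF above 500 msec in 6/635 = 0.9% (Section 1.4.1.4). None is given for this trigger or for the full path. Assume a trigger rate of 1% to 5%, with 25% to 50% of those subjects completing the remaining steps (failed repeat, later pass, attribution to drug).
- Full path r: 0.01 x 0.25 = 0.0025, to 0.05 x 0.50 = 0.025.
- P(at least one) = 1 - (1 - r)^n. For n = 3: 0.7% to 7.3%. For n = 6: 1.5% to 14.1%.

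**6. Effect on dose finding.** As an upper bound, suppose the ipilimumab cut removed the whole 8.1% rate of grade 3-4 dose-limiting effects quoted for ipilimumab in Section 1.1.1.
- Fall in expected DLT rate = 0.081 x r = 0.0002 to 0.0020, or 0.02 to 0.2 percentage points.
- P(0 of 3) at an 18% DLT rate = 0.82^3 = 0.5514. It rises to 0.5518 (r = 0.0025) or 0.5555 (r = 0.025), which is 0.04 to 0.4 points.

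**The case against.** The strongest case is that this is a guideline cell with ample protection around it. The principal investigator has the final say on QTcF, and Section 3.4 requires discontinuation whenever the investigator judges continuation not to be in the subject's interest, so panobinostat can already be stopped. Resumption comes only after electrolyte correction, a concomitant-medication check, sponsor notification and a passing triplicate. A second failure, or drug-related QTcF of 500 msec or more, ends treatment. Section 5.3 calls the scheduled ECGs a minimum. Section 1.4.1.4 reports mean QTc changes under 10 msec across oral doses and no torsade de pointes with intermittent dosing. Other QTcF paths also resume at full dose: a same-day pass on Day 5, and a repeat pass in Cycle 2 and beyond, even at 20 mg. Finally, the frequency is assumed.

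Much of this stands as a limit on harm and frequency. It does not remove the defect. Discretion permits a correction but does not supply one. The full-dose paths concern prolongation that was not confirmed on repeat; here it was confirmed, and the plan itself calls for a reduction. The reassuring Section 1.4.1.4 figures are averages, and its six cases above 500 msec all arose on the every-week oral schedule, which this trial uses. A broader conflict also exists between the dose level #1 sentence and Table 4.3's cohort 1 row, but settling it either way would not lower panobinostat.

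**Conclusion.** The concern holds. For cohort 1 only, the written default after confirmed, drug-related QTcF prolongation on Day 5 restarts panobinostat unchanged and, from Day 22, reduces the drug with no stated QT signal. The dose changes (0% for panobinostat, 12 to 6 mg/kg for induction ipilimumab) follow directly from the tables and the infusion schedule. The counts of 6 and 14 unchanged doses rest on the assumed weekday pattern. The 0.7% to 14.1% chance of meeting the case rests wholly on the assumed trigger and completion rates. The event is probably rare and its effect on escalation decisions is negligible. The reason to act is subject safety, set against a very small cost of repair.

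**What to change.** Add one footnote to Tables 4.2 and 4.3. For cohort 1, drug-related QTcF prolongation that meets the Day 5 reduction criterion leads to discontinuation of panobinostat, because 5 mg is the lowest capsule strength (Section 4.1.1.2). Ipilimumab is not reduced to 1 mg/kg for QTcF. Leave cohort -1's Off Study rule and all other rows as they are. A less frequent panobinostat schedule would be an alternative, but it would need a regimen that the plan does not define.

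The footnote adds no visits or subjects. Its cost is that a rare cohort 1 subject whose ECG has recovered stops panobinostat. Section 4.3.1 replaces only subjects who miss doses for reasons other than drug-related toxicity, so this subject stays in the DLT denominator after about 2 of 36 planned panobinostat doses (Days 1 and 3, out of 12 weeks x 3, on the same assumed pattern). The cohort 1 DLT review should note any such subject, so that the cohort is not read as safer than the exposure supports.

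### Table 4.2, Cycle 2 and beyond: the > 480 msec row has no upper limit, so a first QTcF of 500 msec or more can fall under both a repeat-and-dose instruction and a discontinue instruction

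*Combined protocol and SAP*

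**What the plan says.** Table 4.2 in Section 4.3.6 has a block for Cycle 2 and beyond with two triggers.

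- **Lower row**, "Average QTcF > 480 msec". Staff check and correct electrolytes and review concomitant medication. If an abnormality is noted, they repeat the three pre-dose ECGs. If the repeat fails: "Do not meet criteria again, discontinue patient from the study". If it passes: "Do meet criteria for dosing; administer study drug treatment If, however, it was determined", where the last words open the exception for an electrolyte or medication cause (omit the dose, continue at the same level on the next dosing day).
- **Upper row**, "Average QTcF ≥ 500 msec". Staff check and correct electrolytes, then "Discontinue patient from study therapy". The same exception applies. There is no route from a passing repeat ECG to dosing.

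Both rows act on a triplicate described as "If required: Pre-dose on day 1 of each cycle 3 ECGs separated by at least 5 minutes"; Table 5.12 schedules a single ECG after Cycle 1 Day 5.

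The Cycle 1 Day 5 block has the same two tiers, but its lower trigger reads "≥ 480 msec to < 500 msec OR > 60 msec increase from baseline average". Its first clause is capped at 500 msec; its second clause is not.

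The text before the table assigns "Any final decisions concerning dose modifications or permanently discontinuing the patient from study drug due to QTcF prolongation" to the principal investigator's assessment. Section 5.3 calls the QTc modifications recommended.

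**The concern.** A cardiac stopping threshold should give one action for one reading. In the Cycle 2 block the lower trigger contains the whole of the upper one, and the two rows do not always lead to the same action. Where they differ, one gives panobinostat and the other ends treatment. Section 1.4.1.4 describes QT prolongation as a known class effect and treats QTcF above 500 msec as clinically relevant.

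The practical stake is clarity. Section 9.1 requires the study to be run as described and significant deviations to be documented. In the overlap, staff cannot tell from the table which action follows the protocol and which departs from it.

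**Working it through.** The plan states no figure to reproduce here, so the check compares triggers and actions.

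**1. Triggers, Cycle 2 and beyond.** Let Q be the first triplicate average in msec.

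- Lower row: Q > 480, that is (480, ∞).
- Upper row: Q ≥ 500, that is [500, ∞).
- Overlap: [500, ∞), the whole upper row.

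**2. Actions in the overlap.**

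| Situation, first Q ≥ 500 | Lower row | Upper row | Same action? |
|---|---|---|---|
| Electrolyte or medication cause | Omit dose, continue at same level | Omit dose, continue at same level | Yes |
| No such cause, repeat above 480 | Stop | Stop | Yes |
| No such cause, repeat 480 or less | Give dose | Stop | **No** |

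Example: first average 510, repeat 470, no cause found. 510 > 480 and 510 ≥ 500, so both rows apply; 470 ≤ 480, so the repeat passes. The smallest fall that produces the conflict is 500 − 480 = 20 msec.

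**3. Dependence on one phrase.** The lower row makes the repeat conditional on an abnormality being noted. The column that holds the thresholds is headed as the abnormality noted, so the natural meaning is the QTcF value itself, and step 2 uses that reading. If the phrase means an abnormality found in the electrolyte and medication check, the conflict needs one that is found and then judged not to be the cause. That is narrower still.

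**4. Cycle 1 Day 5.** Let b be the baseline average. The uncapped clause is met when Q > b + 60.

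- With b = 440 and Q = 510, the rise is 510 − 440 = 70 > 60, and 510 ≥ 500. Both Day 5 rows apply.
- For any b below 440, b + 60 < 500, so every Q ≥ 500 meets both rows.
- At b = 450, the highest average allowed by the Cycle 1 Day 1 dosing limit, the clause starts above 510. Readings from 500 to 510 meet only the upper row.

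The Day 5 lower row also allows dosing after a passing repeat, while the upper row discontinues unless electrolytes or medication are the cause.

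**5. How often the rows come into use.** Scheduled ECGs under the Cycle 2 block fall on Day 42 + 1 = 43, then Day 85 and every 84 days (169, 253, 337). That is five in the first 365 days on treatment, one of them inside the 84-day DLT window. Section 1.4.1.4 reports QTcF above 500 msec in 6/635 = 0.94% of patients on intermittent oral dosing, all on the every-week schedule, whose own denominator is not given. Neither figure estimates the frequency of the conflict.

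**6. After the change.** Cycle 2 triggers become (480, 500) and [500, ∞), with an empty overlap. With the 60 msec clause limited to Q < 500, the Day 5 triggers are disjoint too. Test values of 500, 510 and 520 then meet only the upper row in either block.

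**The case against.** The strongest reply is that ordinary reading settles the matter. The rows are graded tiers. If the repeat-and-dose route also governed readings of 500 msec or more, the unconditional stop in the upper row would lose its force. Applying the more specific row gives both rows effect and matches the Day 5 action at that level. In addition, this is a single-site trial, the principal investigator has the final say, and the protocol presents the table as guidance. This stands as a limit on harm: a reader would probably reach the right action. But no text states the precedence, and a named decision-maker does not make the table consistent.

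A second reply is that the Day 5 block is a poor model, because its own lower row overlaps the upper one through the 60 msec clause. This also stands. The Day 5 cap suggests what was intended for Cycle 2 but does not prove it, and a repair of Cycle 2 alone would be partial.

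A reader might infer that the protocol freely permits dosing at 500 msec or more. It does not: the lower row requires the electrolyte and medication check and a passing repeat triplicate first.

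A reader might also want the screening exclusion (QTc above 500 msec) aligned with the Day 1 limit of 450 msec. The stricter limit already governs dosing. Moreover, judging eligibility on a triplicate that may be taken on Day 1 could move that decision past registration (Sections 4.2 and 5.3).

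**Conclusion.** The point holds in a narrow form. As printed, the Cycle 2 rows conflict when three conditions meet: a first average of at least 500 msec, no electrolyte or medication cause, and a repeat of 480 msec or less. This assumes that the abnormality in the lower row is the QTcF abnormality; on the other reading the conflict is narrower. The Day 5 block has a related overlap through its 60 msec clause.

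The case is rare, and the documents support no frequency for it. A reader might take 6/635 as that frequency, but it counts readings above 500 msec on two pooled schedules and says nothing about repeats or causes. Section 1.4.1.4 also places the mean QTc changes in the first week of Cycle 1, before the Cycle 2 rows apply.

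A reader might also infer an effect on the dose-escalation results. The documents do not support that. DLTs are defined in Section 4.3.3 by grade, duration and relation to study drug, without reference to which row of Table 4.2 was followed. No DLT, mTPI or sample-size figure is affected. This is a minor correction to a safety instruction.

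**What to change.** Make two edits in Table 4.2:

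1. Cycle 2 and beyond, lower row: change the trigger to an average QTcF > 480 msec to < 500 msec.
2. Cycle 1 Day 5, lower row: limit the clause on a rise of more than 60 msec from baseline to averages < 500 msec.

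A reading of 500 msec or more then leads only to the discontinue row, with its existing electrolyte and medication exception. The cost is two table cells, with no change to visits, ECG schedule, eligibility, escalation rules or sample size.
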